9. STATISTICAL METHODS

9.1. Determination of sample size

The study sample size was determined by the revised study design while maintaining an adequate study power to achieve all co-primary objectives previously discussed with CBER. The multiplicity issue was dealt with by controlling the global α at the level of 0.05 for all associated statistical hypotheses. This reduced number will also allow for enrolment of the minimum number of subjects exposed to rMenB+OMV NZ to fulfill initial Pediatric Study Plan (iPSP) commitment. The sample sizes were also calculated for the secondary objectives to evaluate the non-inferiority of RIV antigens. The evaluation will be performed by calculating the between-group differences/ratios and their 2-sided 95% CI. Therefore, no multiplicity was adjusted for the secondary objectives.

Study Sample Size Determination by Co-Primary Objectives

For the immune response to PCV13, sample size calculations were based on data from the PCV13 package insert and for the immune response to rMenB+OMV NZ sample size calculations were based on data from the previous GSK (legacy Novartis) V72P13 and V72P13E1, and from V72_56 study.

Using the procedure described in this section, the power for the study is presented in [Table 17](#). In case of 40% drop-out rate and 1200 subjects to be enrolled in a 2:1 ratio, it's assumed that 480 evaluable subjects from Group MenB+PCV and 240 evaluable subjects from Group Placebo+PCV could participate with data to the analyses. For PCV13 antigens a sample size of 240 will have approximately 99% power to show non-inferiority for all antigens. For MenB strains it's assumed that 480 evaluable samples from Group MenB+PCV will be evaluated in the analyses. With 240 per group for PCV13 antigen tests and 480 evaluable subjects from Group MenB+PCV for rMenB+OMV NZ strain tests, there is approximately 99% probability to reject all 23 null hypotheses, and to claim that the primary objectives of the study will be met according to the predefined success criteria.

Table 17 Power to Show Non-Inferiority PCV13 Co-Primary Objective and Sufficiency rMenB+OMV NZ Co-Primary Objectives

Co-Primary Objective	Power
Non-inferiority for GMCs for 13 antigens after the 3 rd vaccination	99.0%
Sufficiency for % of subjects with titers \geq LLOQ per each strain and all 4 strains combined (composite response) after the 3 rd vaccination	99.8%

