Sufficiency for % of subjects with hSBA titers \geq 8 (for strains M14459, NZ98/254, M13520) and \geq 16 (for strain 96217) individually and all 4 strains combined (composite response) after the 4 th vaccination	>99.999%
Probability of rejection of all 23 null hypotheses.	98.8%

The power was estimated using simulations: 10.000 simulations per case. SAS 9.4 was used for the calculations.

A short summary on the steps of simulation is presented below, in the example of 40% drop-out. The definition for families is given in [Section 9.5.3.1](#).

In total 10.000 simulations were performed, each simulation consisted of:

- For testing Family 1, 240 normal distributed data were drawn for two groups and hence two times thirteen antigens, according to the ratio of GMC and the SD, as described below [Table 18](#). For PCV13, a GMC ratio of 0.8 was assumed. Correlation structure was made for between-antigen correlation of 0%.
- For testing Family 2 and 3, 480 normal distributed data were drawn for one single group and for the four strains, according to the GMTs (for post 3rd dose) and GMTs (for post 4th dose), as shown in [Table 19](#), and the SDs as described below [Table 18](#). Correlation structure was made for between-antigen correlation of 0%.
- Testing of Family 1: Shifted one-sided t-test was used to test the hypotheses and output the p-values (for the power calculation no center effect was assumed).

- d. P-values were compared with the Family Wise Error Rate (FWER) to conclude on whether the null hypotheses were rejected or not. FWER for Family 1 is initially set to be 1/3 of the full alpha, which is rounded to 0.017. The FWER for Family 2 is 0.033 and the initial FWER is 0 for Family 3. No multiplicity adjustment was performed within a family. Within family 1 all thirteen antigens were tested with the full FWER for family 1. If one or more test fail to reject the hypothesis for the antigen, family 1 fails. Consequently the alpha of family 1 will not be propagated (see bullet h. below).

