 - 2) If Family 2 had succeeded and Family 1 not, then propagate ½ FWER from Family 2 to Family 3 and the other ½ FWER to Family 1, and re-test Family 1 with the new FWER which is the sum of the original FWER from Family 1 plus the ½ of FWER from Family 2. If the null hypothesis were rejected during the 2nd time test, then claim the success of Family 1 and propagate full FWER to Family 3; otherwise Family 1 fails and proceed with Family 3 testing with the ½ of FWER propagated from Family 2.
 - 3) If both Family 1 and Family 2 had succeeded, then the FWER from both families were propagated to Family 3, and proceed to test Family 3;

- 4) If both Family 1 and Family 2 had failed, then no FWER will be propagated to Family 3, and we stop the testing globally.
- i. Testing of Family 3: with the given FWER, if the LCL is greater or equal to 0.6 for each of strain M14459, 96217 and NZ98/254, M13520, and greater or equal to 0.5 for the composite endpoint, then Family 3 is claimed for success.
- j. Add a loop on top of the aforementioned steps for 10.000 times simulation, summarize the probability of have all hypotheses rejected for each and all families, and the probability to meet all the primary objectives.

Based on the immune response observed in infant data from V72P13E1 and the PCV13 package insert, the following assumptions were made for the calculations:

1. As estimate for the SD of the different antigens and strains was taken the upper 80% CI limits of the common standard deviations for the \log_{10} titers observed in GSK (legacy Novartis) study V72P13E1 and \log_{10} ELISA concentrations observed from PCV13 studies. SDs that were used in the sample size calculations are presented in the table below.

Table 18 Two-sided 80% Upper Confidence Limit of Standard Deviations

	80% UCL of SDs	
rMenB+OMV NZ strains	Post 4 th vaccination (SDs of GMT)	Post 3 rd vaccination (SDs of GMT)
M14459	0.45097	0.32193
96217	0.63454	0.36900
NZ98/254	0.53796	0.51670
M13520 ²	0.36477	0.45023
PCV13 antigen ¹	Post 3 rd vaccination (SDs of GMC)	
1	0.36629	
3	0.41572	
4	0.34261	
5	0.43567	
6A	0.39552	
6B	0.44974	
7F	0.34352	
9V	0.32548	
14	0.32445	
18C	0.33550	
19A	0.24439	
19F	0.45638	
23F	0.37567	

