¹Estimated SDs for PCV13 antigens are the upper confidence limit of 2-sided 80% CI of back-calculated SDs, based on information (degree of freedom, 95% CI) provided on table 17 of *Prevnar13 Package Insert* (dated on July 2016) and assuming the underlying SDs fulfill a t-distribution.

² The assumptions for M13520 are cited from study V72_56 (205240) ad-hoc analysis on additional NHBA strains.

2. Underlying GMC ratios for each PCV13 antigens is assumed as 0.8.
3. For the sufficiency objectives, the following mean ($\log_{10}(\text{GMT})$) were used in simulation based on observed data from previous studies (studies V72P13 and V72P13E1 and V72_56):

Table 19 GMTs at One Month Post 3rd Dose and GMRs at One Month Post 4th rMenB+OMV NZ Vaccination

rMenB+OMV NZ strains	GMTs* Post 4 th vaccination	GMTs* Post 3 rd vaccination
M13520	1.41225	1.10501
NZ98/254	1.57978	1.15836
M14459	1.53148	1.26400
96217	3.06183	2.66753

*log-scale

4. The LODs and LLOQs associated with the 4-fold definition are assumed to be:

Table 20 Limits of Detection and Lower Limits of Quantitation for rMenB+OMV NZ strains

rMenB+OMV NZ strains	LOD	LLOQ
M13520	4	4
NZ98/254	4	6
M14459	3	5
96217	6	15

LOD: lower limit of detection, LLOQ: lower limit of quantitation.

Note: Other than for strain M13520, these LODs and LLOQs were cited from the latest lab assay validation report released in 2018. For strain M13520, the LOD and LLOQ are validated and cited from the latest laboratory assay validation report released in 2020.

5. That each comparison is statistically independent.

In conclusion, assuming a 40% drop-out rate in this age group, a total of 1200 subjects to be enrolled in a 2:1 ratio, which will lead to 480 subjects evaluable in Group MenB+PCV and 240 subjects evaluable in Group Placebo+PCV, there will be 99% power to conclude that:

- 13 PCV13 antigens will be shown non-inferiority of PCV13 vaccine when co-administrated with rMenB+OMV NZ vaccine, compared to PCV13 vaccine that is administered alone, at one month post 3rd vaccination
- The percentage of subjects with titers \geq LLOQ is more than or equal to 60% for strain M14459, 96217, NZ98/254 and M13520, and more than or equal to 50% for all 4 rMenB+OMV NZ strains at one month post 3rd vaccination.
- Percentage of subjects with 4-fold increase is more than or equal to 75% for strain M14459, 96217, NZ98/254 and M13520, and more than or equal to 65% for all four rMenB+OMV NZ strains, at one month post 4th vaccination.

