9.5.3.2. Statistical Methods

For statistical analyses of the concentration/titer data, the concentrations/titers will be logarithmically transformed (base10), to fulfill Gaussian distribution assumption.

The Global Type I error rate will be controlled globally at a 5%/2.5% level (2-/1-sided, respectively). If applicable, the α -level will be propagated as described below [Hommel, 2007]. The sequence of testing the different families is presented in [Figure 2](#) and described in more detail thereafter.

Figure 2 Testing Strategy for Three Families with Corresponding α Propagation

The initial α is 0.0167 (2-sided) for Family 1 and 0.033 (2-sided) for Family 2, while it is zero for Family 3.

Step 1: Family 1 and Family 2

- Start test Family 1 and Family 2 as the first step.
 - For testing Family 1 the hypotheses per antigen the p-values will be obtained from an ANOVA model, with vaccination group and center as independent variables and log transformed titers/concentrations as response variable. The null hypotheses will be rejected if the p-values < FWER for all thirteen antigens.
 - For testing Family 2, if the lower limits of the 2-sided 96.67% CIs are greater or equal to the sufficiency margins for each of the four strains and composite endpoint, then Family 2 is successful. Otherwise, Family 2 fails.
- If Family 1 had succeeded and Family 2 not, then propagate $\frac{1}{2}$ FWER from Family 1 to Family 3 and the other $\frac{1}{2}$ FWER to Family 2, and re-test Family 2 with the new FWER which is the sum of the original FWER from Family 2 plus the $\frac{1}{2}$ of FWER from Family 1. If the null hypothesis were rejected during the 2nd time test, then claim the success of Family 2 and propagate full FWER to Family 3; otherwise Family 2 fails and proceed with Family 3 testing with the $\frac{1}{2}$ of FWER propagated from Family 1.
- If Family 2 had succeeded and Family 1 not, then propagate $\frac{1}{2}$ FWER from Family 2 to Family 3 and the other $\frac{1}{2}$ FWER to Family 1, and re-test Family 1 with the new FWER which is the sum of the original FWER from Family 1 plus the $\frac{1}{2}$ of FWER from Family 2. If the null hypothesis were rejected during the 2nd time test, then claim the success of Family 1 and propagate full FWER to Family 3; otherwise Family 1 fails and proceed with Family 3 testing with the $\frac{1}{2}$ of FWER propagated from Family 2.

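### Table 17's two hSBA power rows do not match the protocol's own inputs and look transposed; and with the LLOQs the SAP will apply, post-3rd power falls to about 82% at the stated 0% correlation

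*Protocol*

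**What the plan says.** Table 17 in Protocol 9.1 lists three co-primary powers and their joint value:

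- PCV13 non-inferiority: 99.0%.
- hSBA ≥ LLOQ ("per each strain and all 4 strains combined (composite response) after the 3"rd vaccination): 99.8%.
- hSBA ≥ 8, or ≥ 16 for strain 96217 ("individually and all 4 strains combined (composite response) after the 4"th vaccination): >99.999%.
- All 23 null hypotheses rejected: 98.8%.

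The simulation behind the table is described in the same section: "For testing Family 2 and 3, 480 normal distributed data were drawn for one single group and for the four strains". The 480 comes from 800 enrolled, "assuming a 40% drop-out rate in this age group". On dependence the text says "Correlation structure was made for between-antigen correlation of 0"%.

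On alpha, "The FWER for Family 2 is 0.033 and the initial FWER is 0 for Family 3", and Protocol 9.5.3.2 confirms that these are two-sided. Family 2 is post-4th and Family 3 is post-3rd. On what reaches Family 3: "If both Family 1 and Family 2 had succeeded, then the FWER from both families were propagated to Family 3".

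The post-3rd responder cut-off is the LLOQ. Table 20 sets it at 4 (M13520), 6 (NZ98/254), 5 (M14459) and 15 (96217). SAP 5.3.2 lists the limits that the analyses will use as 6, 6, 5 and 14 in the same order.

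**The concern.** Section 9.1 gives every input needed to reproduce the two hSBA rows, and neither reproduces as labelled. Each printed value is what the inputs yield for the other row. Table 17 therefore names the wrong hSBA family as the one with less margin under the protocol's assumptions.

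The second matter is independent of the first. The post-3rd endpoint is defined by the LLOQ, so a higher LLOQ for M13520 directly lowers the expected responder rate for that strain and for the composite. The SAP changes that LLOQ from 4 to 6. Neither document restates the power, and SAP section 8 does not list the change. A reader who relies on the 99.8% or the 98.8% is relying on limits that will not be used.

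**Working it through.** **Inputs.** n = 800 × (1 − 0.40) = 480. Log10 means are from Table 19, SDs from Table 18 and LLOQs from Table 20 or SAP 5.3.2. Margins for the lower limit are 75% per strain and 65% composite post-4th, and 60% and 50% post-3rd. Two-sided alpha is 0.033 for Family 2. For Family 3 it is 0.05 if Families 1 and 2 both succeed.

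**Responder rates.** Rate = Φ((mean − log10 cut-off) / SD).

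| Strain | Post-4th (8; 16 for 96217) | Post-3rd, Table 20 LLOQ | Post-3rd, SAP LLOQ |
|---|---|---|---|
| M13520 | (1.41225 − 0.90309)/0.36477 = 1.396 → 91.9% | (1.10501 − 0.60206)/0.45023 = 1.117 → 86.8% | (1.10501 − 0.77815)/0.45023 = 0.726 → 76.6% |
| NZ98/254 | (1.57978 − 0.90309)/0.53796 = 1.258 → 89.6% | (1.15836 − 0.77815)/0.51670 = 0.736 → 76.9% | 76.9% |
| M14459 | (1.53148 − 0.90309)/0.45097 = 1.393 → 91.8% | (1.26400 − 0.69897)/0.32193 = 1.755 → 96.0% | 96.0% |
| 96217 | (3.06183 − 1.20412)/0.63454 = 2.928 → 99.8% | (2.66753 − 1.17609)/0.36900 = 4.042 → about 100% | about 100% |
| Composite (product, 0% correlation) | **75.4%** | **64.1%** | **56.6%** |

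**Power.** Take the smallest count out of 480 whose Clopper-Pearson lower limit reaches the margin, then the binomial probability of reaching that count. Single-strain powers are all about 100%, so the composite decides each family.

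| Family | Alpha | Count needed | Power |
|---|---|---|---|
| Post-4th | 0.033 | 335 | 99.79% |
| Post-4th, re-tested at 0.033 + 0.017/2 = 0.0415 | 0.0415 | 334 | 99.85% |
| Post-4th, full alpha | 0.05 | 333 | 99.89% |
| Post-3rd, Table 20 | 0.05 | 262 | 99.9993% |
| Post-3rd, Table 20 | 0.033 | 264 | 99.998% |
| Post-3rd, Table 20, half of Family 1's alpha only | 0.0083 | 270 | 99.98% |
| Post-3rd, SAP LLOQ | 0.05 | 262 | **82.4%** |
| Post-3rd, SAP LLOQ | 0.033 | 264 | **77.2%** |

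**Reproducing the printed rows.** The values 99.8% and >99.999% both appear, but for the opposite rows. Wald and Wilson limits, alphas from 0.0167 to 0.10, exchanged SD columns and LOD in place of LLOQ were also tried. None gives >99.999% post-4th (range 99.5-99.97%). With the Table 20 LLOQs none gives 99.8% post-3rd (99.994-99.9999%; 99.94% with the SD columns exchanged). Simulation error is not the explanation: with a true post-4th power of 99.79%, the chance of no failure in 10,000 runs is 0.9979^10,000, below 1e-9.

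**Overall probability.** From the table's own rows, 0.990 × 0.998 × 1.000 = 98.8% in either row order. With the SAP LLOQs it cannot exceed the post-3rd power of 82.4%. As a product it is about 0.990 × 0.998 × 0.824 = 81.4%.

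**Correlation range with the SAP LLOQs.** The composite rate is the probability that four normal variables with a common correlation all exceed their cut-offs.

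| Correlation (assumed) | Post-3rd power at 0.05 | At 0.033 |
|---|---|---|
| 0 (protocol) | 82% | 77% |
| 0.17 | 97% | 96% |
| 0.25 | 99% | 99% |
| 0.457 | >99.9% | >99.9% |

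The values 0.17 and 0.457 bound the range in which the Amendment 4 entry in Appendix C placed most between-strain correlations from the earlier studies. That is superseded text and concerned a different NHBA strain, so the range is indicative only.

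**The case against.** The case for leaving Table 17 alone has several sound parts.

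- The row discrepancy is about 0.2 points between two near-certain figures. The printed post-3rd value errs on the cautious side, and the 98.8%, the sample size of 1200 and the alpha split are unaffected under Table 20. This stands.
- No document shows a transposition. Listing results in family order (Family 2 is post-4th, Family 3 post-3rd) against rows ordered post-3rd then post-4th would produce it, but that is inference. The described procedure also re-tests Family 2 at a larger alpha, so the correct post-4th figure could print as 99.8% or 99.9%. This stands, and it is why the request is to re-run the simulation rather than exchange two labels.
- A reader might infer that the row order conceals the effect of the SAP limits. It does not: either order uses the Table 20 LLOQs, and the fall in power comes only from the changed limits.
- Zero correlation is the pessimistic end for a composite when strains are positively correlated, so 82% should not be quoted alone. This stands, and the range is given. But 0% is the protocol's stated assumption and the basis of its own figures, so like is being compared with like.
- The footnote to Protocol Table 7 foresees changes to validated assay cut-offs. The change itself is therefore not irregular; what is missing is its effect on the stated power.

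**Conclusion.** Both hSBA rows of Table 17 fail to reproduce as labelled and are probably transposed. Post-4th should read about 99.8-99.9%, and post-3rd >99.9% under Table 20. This is a small correction. It would be tempting to say that both co-primary powers are materially wrong, but the documents do not support that.

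The material point is that the 99.8% for post-3rd and the 98.8% overall do not describe the analysis in SAP 5.3.2. Under the protocol's own means, SDs, 480 evaluable subjects and 0% correlation, the SAP limits give about 82% at two-sided 0.05 and 77% at 0.033, which caps the all-23 probability at about 82%. The loss comes entirely from M13520; the change for 96217 from 15 to 14 has no visible effect.

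It would also be too strong to conclude that the trial is underpowered. Modest positive correlation restores 97-99%, and the documents give no current estimate of it for this strain panel. The re-derivation also assumes that the Table 19 means and Table 18 SDs still describe titers under the re-specified limits.

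**What to change.** 1. Re-run the 10,000-run simulation and correct the two hSBA rows of Table 17, stating the alpha at which each family's power is reported. Drop the >99.999% form: no failures in 10,000 runs supports only about 99.97% as a 95% lower bound (1 − 3/10,000).
2. Restate the post-3rd row and the all-23 probability with the SAP 5.3.2 LLOQs. State the between-strain correlation assumed and give a range that includes 0%.
3. Record the LLOQ change from Table 20, and its effect on power, in SAP section 8 or a short protocol clarification.

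The cost is one table re-run and a stated power that becomes less favourable. No endpoint, margin, alpha allocation or sample size has to change.

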
 To demonstrate the immunological non-inferiority of DTaP-HBV-IPV and Hib vaccines when administered concomitantly with rMenB+OMV NZ and PCV13 to healthy infants at 2, 4, and 6 months compared to DTaP-HBV-IPV and Hib vaccines concomitantly administered with PCV13 without rMenB+OMV NZ, in terms of D, T, PT, FHA, PRN, Hep B and Hib, at one month after the 3rd vaccination. 
Criterion: The immunological non-inferiority will be demonstrated if the lower limit of the 2-sided 95% CI for the between-group differences is greater than the pre-specified margin^t for each antigen at one month after 3rd vaccination.
	
 At 1 month after the 3rd vaccination (Day 151): 
 GMCs against the 3 pertussis antigens (Pertussis toxin [PT], pertactin [PRN], filamentous hemagglutinin [FHA]). Percentages of subjects with anti-HBs antibody concentrations ≥10 mIU/mL. Percentages of subjects with anti-diphtheria and anti-tetanus concentrations ≥0.1 IU/mL. Percentages of subjects with anti-PRP concentration ≥0.15 µg/mL and ≥1 µg/mL.

 To demonstrate the immunological non-inferiority of MMR and VV vaccines when administered concomitantly with rMenB+OMV NZ and PCV13 to healthy subjects at 12 months compared to 	
 At 1 month after the 4th vaccination (Day 331): 
 GMCs against measles, mumps, rubella and VZV antigens.

CONFIDENTIAL

205239 (MENB REC 2ND GEN-023 [V72_57])

Protocol Amendment 8 Final

Objectives	Endpoints

MMR and VV vaccines concomitantly administered with PCV13, without rMenB+OMV NZ, at one month after vaccination.
 
Criterion: The immunological non-inferiority will be demonstrated if the lower limit of the 2-sided 95% CI for the between-group ratio of GMCs is >0.67 at one month after the MMR and VV vaccinations.
	

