5.2.3. Allocation of subjects to assay subsets

For the analysis of the immune responses to the RIV antigens, subjects in each of the 2 study groups will be randomly assigned to different immunogenicity subsets. The assignment of the immunogenicity subsets will be performed by a second randomization, whereas the first randomization will be performed at the enrolment to assign subjects to Group MenB+PCV or Group Placebo+PCV.

Group MenB+PCV: All 800 subjects will be randomly assigned into one of the 3 immunogenicity subsets:

- Subset A1: 400 subjects
- Subset A2: 200 subjects
- Subset A3: 200 subjects

Group Placebo+PCV: A total of 400 subjects will be randomly assigned into 2 immunogenicity subsets:

- Subset B1: 200 subjects
- Subset B2: 200 subjects

The different subsets against which the different antigens will be tested are described in [Table 9](#). Testing of diphtheria, tetanus, pertussis, polio, HepB and Hib antigens will be performed at Visit 4 (post-3rd vaccination). Testing of MMR and VV will be done at Visit 5 (pre-4th vaccination) and Visit 6 (post-4th vaccination). In addition, subjects from subset B1 (200 subjects) will also be tested against the 4 serogroup B strains at all 3 timepoints in order to maintain the observer-blindness of the study during the blood sample testing.

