Determination of the Immunogenicity Subsets Sizes for the Secondary Objectives:

As described in detail in [Table 9](#), due to limited serum volume available subjects will be randomly assigned to test different sets of RIV antigens. Subjects will either be assigned to subset A1, A2, A3 in Group MenB+PCV or assigned to subset B1 and B2 in Group Placebo+PCV (see Section [5.2.3](#)). The below tables ([Table 21](#) and [Table 22](#)) show the likelihood to achieve non-inferiority for each of the RIV antigens (excluding polio) with the proposed sample sizes for immunogenicity subsets.

Table 21 Non-inferiority to Each Individual Antigen (excluding polio antigens) in Pediarix and Hiberix, at One Month After 3rd Dose of rMenB+OMV NZ

Component	Endpoint	Non-inferiority Margin	Reference		# Evaluable Subjects per Immunogenicity Subset (MenB group/Placebo group)*	Power
			Difference in %/ratio (Co-ad vs routine)	% in Routine group or SD		
Diphtheria	%≥0.1IU/mL	10%	Diff=0%	99.4%	240/120	>99.9%
Tetanus	%≥0.1IU/mL	5%	Diff=0%	100%	240/120	>99.9%
PT	GMC	1.5	Ratio=0.8	SD: 0.31535	480/240	88.7%
FHA	GMC	1.5	Ratio=0.84	SD: 0.3111	480/240	98.3%
PRN	GMC	1.5	Ratio=0.83 ^b	SD: 0.43427	480/240	79.1%
HepB	%≥10.0mIU/mL	10%	diff=-2%	97.7%	120/120	93.5%
Hib	%≥0.15µg/mL	5%	diff=0% ^a	96.6%	360/240	91.2%
	%≥1µg/mL	10%	diff=0%	81.2%	360/240	86.7%

Abbreviations: SD, standard deviation; GMC, geometric mean concentrations; PT, pertussis toxin; FHA, Filamentous hemagglutinin; PRN, pertactin; HepB, Hepatitis B; Hib, Haemophilus influenzae type B; diff, difference

Note: The sources are V72P13 clinical study report and the package insert of vaccines, unless otherwise indicated.

SDs for Pertussis were taken from GSK study Hib-97.

^aSource: V72P12 CSR.

^b Source: V72P16 Table 14.2.1.14 Group B+OMV versus MenC.

* Considering an estimated drop-out rate of 40%.

Table 22 Non-inferiority to Each Individual Antigen in MMR II and Varivax, at One Month After 4th Dose of rMenB+OMV NZ

Component	Endpoint	Non-inferiority Margin	Reference		# Evaluable Subjects per Immunogenicity Subset (MenB group/Placebo group)*	Power
			Ratio (co-ad vs routine)	SD		
Measles	GMC	1.5	ratio=0.9	SD: 0.45 ^a	480/240	95.5%
Mumps	GMC	1.5	ratio=0.9	SD: 0.38 ^a	480/240	99.1%
Rubella	GMC	1.5	ratio=0.9	SD: 0.34 ^a	480/240	99.8%
Varicella	GMC	1.5	ratio=0.9	SD: 0.45 ^b	480/240	95.5%

a Reference for sample size calculation: GSK Study MMR-161.

b Reference for sample size calculation: GSK Study MMR-160.

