9.5.4.1. Statistical Methods

Concentration and titer data will be summarized by vaccine group, strain and time point. Additionally, within-subject GMRs will be computed for GMTs at one month after 4th vaccination versus pre-4th vaccination. As for GMTs, the GMRs and 95% CIs will be computed by exponentiating (base 10) the corresponding means and 95% CIs from an ANOVA model.

For the binary variables, for example, percentage of subjects with hSBA titer \geq LLOQ, percentage of subjects with serum pneumococcal anti-capsular polysaccharide IgG ≥ 0.35 $\mu\text{g/mL}$, the number and percentage of subjects and associated 2-sided 95% Clopper-Pearson CIs will be computed for each antigen/strain by vaccine group and by time-point. Between group-differences with 95% CIs will be derived using the Miettinen and Nurminen method [Miettinen, 1985].

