#### *Statistical Methods*

Concentration and titer data will be summarized by vaccine group, strain and time point. Additionally, within-subject GMRs will be computed for GMTs at one month after 4th vaccination versus pre-4th vaccination. As for GMTs/GMCs, the GMRs/GMCs and 95% CIs will be computed by exponentiating (base 10) the corresponding means and 95% CIs from an ANOVA model.

For the binary variables, for example, percentage of subjects with hSBA titer  $\geq$  LLOQ, percentage of subjects with serum pneumococcal anti-capsular polysaccharide IgG  $\geq 0.35$   $\mu\text{g/ml}$ , the number and percentage of subjects and associated 2-sided 95% Clopper-Pearson CIs (available in SAS Procedure PROC FREQ, [Frank, 2009 ;Clopper, 1934]) will be computed for each antigen/strain by vaccine group and by time-point.

Between group-differences with 95% CIs will also be derived using the Miettinen and Nurminen method [Miettinen, 1985].

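### Table 21 gives 93.5% power for hepatitis B non-inferiority, but the planned Miettinen-Nurminen interval delivers about 81.5% at the same inputs

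*Protocol*

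**What the plan says.** Protocol Section 9.1 introduces Tables 21 and 22 by saying that they "show the likelihood to achieve non-inferiority for each of the RIV antigens (excluding polio) with the proposed sample sizes for immunogenicity subsets". The hepatitis B row of Table 21 reads "≥10.0mIU/mL 10% diff=-2% 97.7% 120/120 93.5" (percent). So the control rate is 97.7%, the assumed difference is -2 points, the margin is 10 points, there are 120 evaluable infants per group, and the power is 93.5%. The table footnote, "Considering an estimated drop-out rate of 40" percent, explains the 120: Section 5.2.3 lists "Subset B2: 200 subjects", and 200 × 0.6 = 120. Table 21 names no power formula.

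The success criterion in protocol Section 2 is that the "lower limit of the 2-sided 95% CI for the between-group differences is greater than the pre-specified margin" for each antigen. Section 9.1 adds that "no multiplicity was adjusted for the secondary objectives", so each comparison runs at one-sided 0.025.

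On the interval, protocol Section 9.5.4.1 says "Between group-differences with 95% CIs will be derived using the Miettinen and Nurminen method", and the Statistical Methods part of SAP Section 5.3.1.4 says "Between group-differences with 95% CIs will also be derived using the Miettinen and Nurminen method". SAP Section 5.3.2 repeats the method and adds that the differences are adjusted for center.

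**The concern.** With response rates close to 100%, the two methods behave differently. The Wald formula takes its variance from the assumed rates, 95.7% and 97.7%, where binomial variance is small. The Miettinen-Nurminen limit is found by testing a 10-point deficit, and its variance is evaluated at rates constrained to differ by 10 points. That pulls the MenB+PCV rate down to about 89%, where the variance is much larger. Power calculated for the first method therefore overstates what the second will deliver.

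The DTaP-HBV-IPV and Hib objective is met only if every antigen passes, so a reader uses Table 21 to see where it is most likely to fail. As printed, hepatitis B ranks fourth highest of the eight rows and looks safe.

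**Working it through.** **Inputs (Table 21; protocol Sections 2 and 9.5.4.1).** Control rate 0.977. MenB+PCV rate 0.977 - 0.02 = 0.957. Margin 0.10. n = 120 per group. Two-sided 95% interval, z = 1.96.

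**Step 1: reproduce the stated figure.** Unpooled normal approximation:

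- SE = √(0.957 × 0.043/120 + 0.977 × 0.023/120) = 0.02303
- Power = Φ((0.10 - 0.02)/0.02303 - 1.96) = Φ(1.514) = 93.5%

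The same formula reproduces both Hib rows (360/240):

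- At or above 0.15 µg/mL: SE = √(0.966 × 0.034 × (1/360 + 1/240)) = 0.01510, and Φ(0.05/0.01510 - 1.96) = 91.2%
- At or above 1 µg/mL: SE = √(0.812 × 0.188 × (1/360 + 1/240)) = 0.03256, and Φ(0.10/0.03256 - 1.96) = 86.7%

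All three agree with Table 21, so its method can be identified with some confidence.

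**Step 2: approximate the score-based power.** At the assumed rates, the maximum-likelihood rates constrained to a 10-point deficit are 0.886 and 0.986:

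- Constrained SE = √((0.886 × 0.114 + 0.986 × 0.014)/120) ≈ 0.0308, against 0.0230 above
- Power ≈ Φ((0.08 - 1.96 × 0.0308)/0.0230) ≈ 80.2%

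**Step 3: exact power of the planned interval.** Take all 121 × 121 outcomes of Bin(120, 0.957) and Bin(120, 0.977), and sum the probabilities of those whose lower limit exceeds -10%:

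| Method, one-sided 0.025 | Power |
|---|---|
| Table 21 | 93.5% |
| Wald interval, enumerated | 89.8% |
| Newcombe interval, enumerated | 81.8% |
| Miettinen-Nurminen interval, enumerated | 81.5% |

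The Miettinen-Nurminen result is 81.5% with or without the N/(N-1) factor, and a simulation of 400,000 draws gives 81.5%. Even the Wald interval, evaluated exactly, falls short of 93.5%. About 165 evaluable infants per group would be needed to reach that figure with Miettinen-Nurminen (93.6%).

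**Step 4: how individual results differ.**

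| MenB+PCV v control responders | Miettinen-Nurminen lower limit | Wald lower limit |
|---|---|---|
| 113/120 v 117/120 | -9.4% | -8.4% |
| 113/120 v 118/120 | -10.1% (fails) | -8.9% (passes) |

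**Step 5: sensitivity to the assumed difference.** Miettinen-Nurminen power at true differences of 0, -1, -2 and -3 points is 98.5%, 93.0%, 81.5% and 65.6%.

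**Step 6: the other percentage rows.** Under Miettinen-Nurminen the Hib rows give 91.7% (stated 91.2%) and 88.2% (stated 86.7%). Diphtheria and tetanus stay above 99.9%. Only hepatitis B moves materially.

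**The case against.** The strongest reply is that 93.5% is not a miscalculation. It follows correctly from the inputs under a standard planning formula, the table is internally consistent, and it never claims to be computed for Miettinen-Nurminen. That is true. The defect is a mismatch between power method and analysis method. But the table is presented as the likelihood of achieving non-inferiority, and at its own inputs the planned analysis does not have that likelihood.

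A second reply is that 81.5% is not the power of the planned analysis either, because SAP Section 5.3.2 adjusts for center. This stands as a caveat: no center sizes or center-level rates are given, so the effect cannot be computed. It does not rescue 93.5%, which ignores center too. The protocol's co-primary simulations likewise assume no center effect (Section 9.1, step c).

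Third, the assumed difference matters as much as the interval, as Step 5 shows. That is fair, and 81.5% is conditional on -2 points. So is the 93.5% it replaces.

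Fourth, the consequences are limited. This is one secondary endpoint, study success can be concluded on the co-primary objectives alone, power stays above 80%, and the plan already accepts 79.1% for pertactin. All of this bears on severity, not on whether the figure is right.

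**Conclusion.** The concern holds. At the inputs in Table 21, the interval that the plan specifies gives about 81.5% power for hepatitis B, 12 points below the stated 93.5%. The risk of missing is 18.5% rather than 6.5%, nearly three times as high, and hepatitis B drops from fourth highest of eight rows to second lowest.

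The plan states no joint power for the objective. As an illustration only, multiply the six rows that are not above 99.9% as if independent: 0.887 × 0.983 × 0.791 × 0.935 × 0.912 × 0.867 = 51%. With 0.815 for hepatitis B, the product is 44%. The two Hib endpoints are measured in the same infants, so independence is not literally true, and positive correlation would raise both products.

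The 81.5% rests on 120 evaluable infants per group, a 97.7% control rate, a true difference of -2 points, and an interval without center adjustment. The co-primary objectives and the validity of the Miettinen-Nurminen analysis are unaffected.

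**What to change.** Restate the hepatitis B power in Table 21 as about 81.5%. Add a footnote that the percentage rows are computed for the two-sided 95% Miettinen-Nurminen interval, without center adjustment. For consistency, the Hib rows would then read 91.7% and 88.2%; diphtheria and tetanus do not change. The cost is a small table edit and a footnote. The hepatitis B figure becomes less favourable. Enrolment, margin and analysis stay as they are.

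Optionally, test hepatitis B in a second 200-infant MenB+PCV subset. With 240/120 evaluable (400 × 0.6 and 200 × 0.6), Miettinen-Nurminen power at the same rates is 98.3%, with no extra enrolment. This would cost additional assays on stored serum. It depends on enough serum remaining, since Section 9.1 gives limited volume as the reason for the subsets, and on the sponsor confirming from Table 9 which subsets are already tested for hepatitis B. The correction to the table does not depend on this option.
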